# 8.3 Adverse Events and Serious Adverse Events

#### 8.3.1 Definition of Adverse Events

This protocol uses the definition of adverse event from 21 CFR 312.32 (a): any untoward medical occurrence associated with the use of an intervention in humans, whether or not considered intervention-related.

#### 8.3.2 Definition of Serious Adverse Events

An adverse event is considered "serious" if, in the view of either the investigator or sponsor, it results in any of the following outcomes: Death, a life-threatening adverse event, inpatient hospitalization or prolongation of existing hospitalization, a persistent or significant incapacity or substantial disruption of the ability to conduct normal life functions, or a congenital anomaly/birth defect. Important medical events that may not result in death, be life-threatening, or require hospitalization may be considered serious when, based upon appropriate medical judgment, they may jeopardize the patient or subject and may require medical or surgical intervention to prevent one of the outcomes listed in this definition.

# 8.3.3 Classification of an Adverse Event

#### 8.3.3.1 Severity of Event

[name] will classify the severity of an adverse event which is a qualitative assessment of the degree of intensity, and will be classified as follows:

• Mild: Does not impact (in any way) the participant's functioning or well-being at work.

- Moderate: Impacts the participant's functioning or well-being at work but is not life-threatening, incapacitating, or job-loss threatening.
- Severe: Severely affects well-being at work; employment termination; lawsuit; fatal, life threatening, permanently disabling; severely incapacitating and/or prolongs inpatient hospitalization.

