#### 8.2 Safety Assessments

In each staff survey, we will assess the following variables. In addition to the questions below, we will also leave open-ended text boxes so people can provide more detail on the incident.

Variables	Description	Levels/range	Justification
Parent backlash	Contact from disgruntled parents/guardians of students because LGBTQ+ inclusivity is in the classroom	Yes/no + Frequency	Parents may not be comfortable with the education their children are receiving and ask questions that educators may not be comfortable or feel safe answering.
	People attack school staff or the school for supporting LGBTQ+ youth	Yes/no + Frequency	This is happening all over the country
School board backlash	School board gets upset or concerned about staff supporting LGBTQ+ youth	Yes/no + Frequency	This is happening all over the country
Suspension or removal from employment	•	Yes/no + Frequency	This is happening all over the country

PLANTS Pilot Trial Protocol STUDY21080	178		Version 1.0 2024.04.05
Censorship of	Promotion and integration of	Yes/no +	This is happening throughout the
-	LGBTQ+ issues, history,	frequency/quantity	country
literature/history/stories	stories into the school		
or removal of books	curriculum could lead to		
with LGBTQ+	attempts to censor that		
	information by parents, school		
	boards, and higher ups in the		
	education system. Oftentimes		
	this has been justified as		
	avoiding "controversial/political		
	topics" in schools. There is the		
	possibility that teachers who		
	teach about		
	"controversial/political" topics		
	could be silenced via threats of		
	losing their jobs.		
Emotional discomfort	Staff are uncomfortable with	Likert 5-point	Some topics may provoke
with PLANTS	the training program.	scale + Open-	discomfort.
		ended	

Study team members will have contact staff and will be able to report adverse events in the appropriate case report form. In the post-trial interviews, we will interview a subset of participants who reported experiencing adverse events. We will ask questions about the AE during interviews, which will help support knowledge of the study intervention effects. We will follow-up with individuals if the event is severe (see the MOP).

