#### 8.4.1 Definition of Unanticipated Problems

This protocol uses the definition of Unanticipated Problems as defined by the Office for Human Research Protections (OHRP). OHRP considers unanticipated problems involving risks to participants or others to include, in general, any incident, experience, or outcome that meets all of the following criteria:

- Unexpected in terms of nature, severity, or frequency given (a) the research procedures that are described in the protocol-related documents, such as the Institutional Review Board (IRB)-approved research protocol and informed consent document; and (b) the characteristics of the participant population being studied;
- Related or possibly related to participation in the research ("possibly related" means there is a reasonable possibility that the incident, experience, or outcome may have been caused by the procedures involved in the research); and
- Suggests that the research places participants or others at a greater risk of harm (including physical, psychological, economic, or social harm) than was previously known or recognized.

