#### Additional Analyses

We will report overall frequency (adding together all the adverse events reported) of adverse events by study arm, followed by the frequency of all types of adverse events by study arm. We will also report the total number of adverse events by severity and average duration, overall and by arm. We will also examine the frequency and percentage of school staff reporting adverse events (which will be counted once only for a given participant). We will also calculate adverse events by school level. We will report study arm-specific percentages of schools that had staff who reported any adverse event and by each type of adverse event.

Study arms will be compared on baseline characteristics (e.g., demographics) using descriptive statistics. We will test for differences in potential confounders between intervention and control arms using baseline staffand school-level data with Rao-Scott chi-square tests for categorical variables and linear mixed models (with a random effect for school) for continuous variables (models adjusting for the clustering of staff within schools).

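### Section 8.3.3.1 separates Mild from Moderate only by impact at work, so a substantial harm confined to life outside work that meets no listed Severe term is graded Mild whatever its intensity

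*Combined protocol and SAP*

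**What the plan says.** Section 8.3.3.1 presents severity as a judgement of how intense an event is, and gives three grades:

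- The lowest grade is worded "Mild: Does not impact (in any way) the participant's functioning or well-being at work", and has no other criterion.
- The middle grade needs some effect on the job to be entered, and is worded "Moderate: Impacts the participant's functioning or well-being at work but is not life-threatening, incapacitating, or job-loss threatening".
- The top grade mixes job-related and other outcomes, and is worded "Severe: Severely affects well-being at work; employment termination; lawsuit; fatal, life threatening, permanently disabling; severely incapacitating and/or prolongs inpatient hospitalization".

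Section 8.3.2 defines a serious event separately, by outcome. The outcomes include "inpatient hospitalization or prolongation of existing hospitalization" and, as a further item in the same list, "a persistent or significant incapacity or substantial disruption of the ability to conduct normal life functions". Section 8.4.1, on unanticipated problems, speaks of "greater risk of harm (including physical, psychological, economic, or social harm". Neither definition is limited to the workplace.

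The grade is used in two places. Section 8.2 says "We will follow-up with individuals if the event is severe (see the MOP"). Under Additional Analyses in Section 9.4.4, the plan says "We will also report the total number of adverse events by severity", overall and by arm.

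**The concern.** The protocol's own safety endpoints include harms that can reach a participant away from school. Section 3 lists backlash on social media, and Section 8.2 asks about attacks on staff who support LGBTQ+ students. If work impact alone decides between the two lower grades, the grade records where the harm was felt and not how intense it was.

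Two uses of the grade are at stake. The severity table by arm would show some substantial harms as Mild. The extra contact that Section 8.2 reserves for severe events would not be triggered for them. If such harms are commoner in one arm, the comparison of severity between arms would shift too; the documents do not say whether they are.

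**Working it through.** The plan states no figure for severity, so the check is a comparison of definitions.

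**Step 1. What separates the grades.**

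| Grade | Criteria tied to work | Criteria not tied to work |
|---|---|---|
| Mild | no impact at work of any kind | none |
| Moderate | some impact at work; no threat of job loss | not life-threatening; not incapacitating |
| Severe | severe effect on well-being at work; loss of employment | lawsuit, death, threat to life, permanent disability, severe incapacity, prolonged hospital stay |

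The only condition for moving from Mild to Moderate is an impact at work. Outside work, the scale has no step between no harm and the listed Severe terms.

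**Step 2. Three cases applied literally.**

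1. *Harassment at home or online, with marked distress, no Severe term met, and no effect on either functioning or well-being at work.* Moderate and Severe are both excluded. Only Mild fits, whatever the intensity.
2. *An event that meets a Severe term without affecting work, such as a lawsuit.* It meets Severe, but it also fits the wording of Mild. No rule says which grade takes precedence.
3. *An event that is serious under Section 8.3.2 but not named in Severe.* See Step 3.

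**Step 3. Severe against the serious-event outcomes.**

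| Outcome in 8.3.2 | Named in Severe? |
|---|---|
| Death; threat to life | yes |
| New inpatient admission | no |
| Prolonged existing hospital stay | yes |
| Persistent or significant incapacity | in part (permanent disability, severe incapacity) |
| Substantial disruption of ordinary life | no |

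Either of the two outcomes marked 'no' can be Mild if work is unaffected.

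**Step 4. What follows from a Mild grade.**

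- *Severity table (9.4.4).* Every event is counted by severity. A Mild event stays in the table, in the wrong row.
- *Follow-up.* Section 8.2 conditions individual follow-up on a severe event. Section 8.3.4 follows all events to resolution without regard to grade. The extra contact in 8.2 is missed; the general follow-up in 8.3.4 is not.
- *Serious-event reporting (8.3.6).* The 48-hour report to the IRB depends on seriousness, so the grade does not affect it.
- *Adverse-event hypothesis (9.4.4).* This is the percentage of PLANTS participants with any event, against a 20% ceiling. Severity does not enter. Nor does it enter the planned precision in Section 9.2, which reproduces without it: 2 × 1.96 × √(0.25/86) = 0.211, against the stated 0.21.

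**The case against.** The strongest reply is that the gap is narrow, and much of that reply stands.

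- **A reader might infer that the scale grades nothing but work.** It does not. Severe contains several terms with no link to work, so the gravest harms can reach it wherever they occur.
- **A reader might infer that affected events vanish from the safety tables or go without follow-up.** The documents do not support this. The events stay in the severity table, in the counts by type and in the number of staff reporting any event, and Section 8.3.4 covers every event. Section 8.2 also refers to a manual of procedures that is not among the documents and may add detail.
- **Mild is stricter than it looks.** It excludes any effect on well-being at work, not only on functioning. A harassed participant who still does the job but feels worse there is at least Moderate. An inpatient admission would often affect work as well.
- **Serious but Mild is not in itself a contradiction.** Severity and seriousness are separate classifications. What is hard to defend is a Mild grade that arises only because the harm was felt elsewhere, when severity is meant to express intensity.
- **Most solicited harms concern the job:** parent contact about the classroom, school-board reaction, suspension or removal, and censorship of materials. Emotional discomfort with the training has its own five-point scale, so its intensity is recorded in any case. Attacks on staff are the main listed item that could act off work.

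These points limit the reach of the gap. They do not supply a grade above Mild for a substantial off-work harm outside the Severe list.

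**Conclusion.** The point holds as a defect in the grading rule. A substantial harm confined to life outside work that meets no Severe term is Mild by definition, and two serious outcomes in Section 8.3.2 have no counterpart in Severe. The consequence is misclassification in the severity table by arm and a missed trigger in Section 8.2. No endpoint, hypothesis or sample-size figure changes.

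The size cannot be estimated from the documents, because they give no share of events felt only outside work. For orientation, if the hypothesised 20% ceiling were reached among the 86 expected PLANTS participants, 0.20 × 86 = 17.2, so about 17 would report any event; those affected would be some subset, from none upward. A reader might be tempted to turn this into an expected count. That would rest on an invented share and would treat a ceiling for any event as a rate of substantial ones. Section 3 expects low incidence and most solicited harms are job-related, so the number is probably small.

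The conclusion assumes that the grades are applied as written and that the manual of procedures does not already correct them.

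**What to change.** 1. In all three grades of Section 8.3.3.1, replace 'at work' with 'at work or in daily life'.
2. Add a sentence that an event meeting any Severe term is graded Severe. This removes the overlap with Mild.
3. Reconcile the Severe list with the outcomes in Section 8.3.2. The first change does not do this alone, because Severe would still name a prolonged hospital stay and not a new admission.
4. Reconcile the follow-up statement in Section 8.2 with that in Section 8.3.4, and check the manual of procedures against both.

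The cost is a wording amendment, with the IRB approval that any amendment needs, and an edit to the adverse-event form. The downside is that a few events move up a grade, so the severity table looks slightly less favourable and a few more participants are contacted.

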# 8.3.3.2 Relationship to Study Intervention

All adverse events (AEs) will have their relationship to study procedures, including the intervention, assessed by an appropriately-trained investigator based on temporal relationship and their scientific judgment. The degree of certainty about causality will be graded using the categories below.

- Related The AE is known to occur with the study procedures, there is a reasonable possibility that the study procedures caused the AE, or there is a temporal relationship between the study procedures and the event. Reasonable possibility means that there is evidence to suggest a causal relationship between the study procedures and the AE.
- Not Related There is not a reasonable possibility that the study procedures caused the event, there is
  no temporal relationship between the study procedures and event onset, or an alternate etiology has
  been established.

# 8.3.3.3 Expectedness

[name] will be responsible for determining whether an adverse event (AE) is expected or unexpected. An AE will be considered unexpected if the nature, severity, or frequency of the event is not consistent with the risk information previously described for the study procedures.

#### 8.3.4 Time Period and Frequency for Event Assessment and Follow-Up

An unsolicited AE would occur without any prompting or in response to a general question such as "Have you noticed anything different since you started the study?" A solicited AE is one that is specifically solicited such as "Have you experienced any problems at work since starting this study intervention?"

The occurrence of an adverse event (AE) or serious adverse event (SAE) may come to the attention of study personnel via surveys, Live Zoom events, interviews, or contact with a study participant or upon review by a study monitor. We will solicit information about AEs directly in surveys and interviews.

All AEs, not otherwise precluded per the protocol, will be captured on the appropriate case report form (CRF). Information to be collected includes event description, time of onset, the PI assessment of severity, relationship to study procedures (assessed only by those with the training and authority to make a report), and time of resolution/stabilization of the event. All AEs occurring while on study will be documented appropriately regardless of relationship. All AEs will be followed to adequate resolution.

Any adverse event that is present at the time that the participant is screened will be considered as baseline and not reported as an AE.

Changes in the severity of an AE will be documented to allow an assessment of the duration of the event at each level of severity to be performed. Documentation of onset and duration of each episode will be maintained for AEs characterized as intermittent.

The PI will record events with start dates occurring any time after informed consent is obtained until 7 (for nonserious AEs) or 30 days (for SAEs) after the last day of study participation. Events will be followed for outcome information until resolution or stabilization.

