#### 2.3.3 Assessment of Potential Risks and Benefits

This is a minimal risk study because the risks that could occur from participation in the intervention or trial are unlikely. Furthermore, we have taken several precautions to minimize potential risks.

Breach of Confidentiality: It is possible that breach of confidentiality may occur. However, we have taken the following active steps to minimize the likelihood of breach of confidentiality. First, all surveys are collected electronically via REDCap, a secure web application for building and managing online surveys and databases.

While REDCap can be used to collect virtually any type of data (including 21 CFR Part 11, FISMA, and HIPAAcompliant environments), it is specifically geared to support online data capture for research studies and operations. Second, we ask that you complete the survey in a private place where no one can see your answers. Surveys can be completed on any computer, tablet, or mobile device, allowing you to complete the surveys when they feel most comfortable. Third, only our research team will have access to REDCap. We will never share their individual answers with any other school staff or administrators. Fourth, for interviews, we will use HIPAA-compliant Zoom accounts and ask that interviews be taken in private quiet spaces. Together, these procedures mitigate the risk of breach of confidentiality.

Emotional discomfort: It is possible that some participants may experience emotional discomfort, embarrassment, or distress while answering questions or as a result of intervention/control materials. We take the following precautions to protect subjects. First, you do not have to answer any question that makes you uncomfortable or that you do not understand. Second, participation in this study is completely voluntary. Third, we will not be asking you questions about sensitive traumatic experiences that may have happened to them. Together, these procedures mitigate the risk of emotional discomfort for school staff.

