#### PLANTS Course: Providing LGBTQ+ Adolescents with Nurturance, Trustworthiness, and Safety

This intervention, PLANTS Course, is an online training program for high school staff. The behavioral outcomes of PLANTS are to train high school staff to: provide interpersonal support and affirmation to SGMY; support LGBTQ+ students in meeting their basic needs; provide educational resources that are inclusive of LGBTQ+ students; provide safe spaces for LGBTQ+ students; promote acceptance of LGBTQ+ students among non-LGBTQ+ students; prevent and reduce bullying, cyberbullying, and harassment of LGBTQ+ students; evaluate and advocate for LGBTQ+ inclusivity and protections in school policies; and maintain the confidentiality of LGBTQ+ students. To achieve these outcomes, we harnessed Information-Motivation-Behavior theory to target high school staff's skills, self-efficacy, knowledge, and outcome expectations. PLANTS uses asynchronous and synchronous online activities with 3 primary sections: Trustworthiness, Safety, and Nurturance. Each section includes, as asynchronous activities, recorded presentations, student testimonials, activities, and downloadable resources for future reference. There are required synchronous Live Zoom Events delivered via Zoom that are 1.5 hours each. Live Zoom Events will be moderated by a trained interventionist and will be tailored to the need of participants. Three Live Zoom Event are offered and participants are required to complete all three. Sections are opened once a month for ~3 months. The modules were developed by my research team, including undergraduate students and graduate students with a variety of academic backgrounds, in partnership with high school staff and other professionals specialize in LGBTQ+ youth or education. We use Canvas Learning Management Software to deliver PLANTS. We will monitor intervention compliance and fidelity via module guestionnaires, Canvas informatics, event attendance, and follow-up survey questionnaires.

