# EMAILS: E-learning to Maximize Academic Inclusion of LGBTQ+ Students

The active control, EMAILS, is an email-based intervention in which existing online resources for supporting, affirming, and protecting LGBTQ+ are emailed to participants. These resources are also provided to intervention participants. The topics covered by EMAILS are similar to those of PLANTS, though there are some unique aspects to PLANTS. This intervention is informed by the Information-Motivation-Behavior theory as well. EMAILS includes the following publicly available materials:

- Adagio Health LGBTQ+ Professionalism Training (https://youtu.be/VX9tDt3gOto)
- Imi (Audience is LGBTQ+ teens, https://imi.guide/)
- The Safe Zone Project (https://thesafezoneproject.com/)

These intervention activities include self-paced modules, YouTube videos, and PowerPoints. There is no direct human interaction in this intervention other than email. EMAILS participants are individually emailed using a duration and pace similar to PLANTS (e.g., lasts 3 months). The intervention takes place entirely online. We will not be doing any tailoring of these materials to specific audiences, other than compiling various resources. We will monitor active control compliance and fidelity via email clicks by sending emails with training links from REDCap to participants, and then participants click on the training links in Qualtrics for tracking purposes. We will also use follow-up survey questionnaires to assess use of EMAILS.

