# **Qualitative Endpoints**

For qualitative interviews, we aim to interview people with a diversity of intervention fidelity, acceptability, usability, feasibility, and appropriateness. This is an exploratory interview study in nature, so idea generation and exploration are the goals (not thematic saturation). We aim to interview PLANTS (n=20-30) and EMAILS (n=10-20) participants, and these sample sizes will provide us with ample information about the CFIR domains.

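### By-arm adverse event tables pool all sources, although one detection route exists only in PLANTS, more interviews are planned there, and event source is not listed for recording

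*Combined protocol and SAP*

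**What the plan says.** Section 8.3.4 lists the routes by which events are noticed: they "may come to the attention of study personnel via surveys, Live Zoom events, interviews, or contact with a study participant", or emerge on review by a study monitor. It then says "We will solicit information about AEs directly in surveys and interviews". The details it lists for the case report form are description, onset, severity, relationship and resolution. How the event came to notice is not among them.

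Two of these routes differ by arm.

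- Live sessions. In the PLANTS description (6.1.1), "Three Live Zoom Event are offered and participants are required to complete all three". Each lasts 1.5 hours and is moderated by an interventionist. For EMAILS, "There is no direct human interaction in this intervention other than email", and 6.1.2 confirms that this arm has no interventionists.
- Interviews. Section 9.2 states: "We aim to interview PLANTS (n=20-30) and EMAILS (n=10-20) participants".

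The additional analyses in 9.4.4 do not separate sources: "We will report overall frequency (adding together all the adverse events reported) of adverse events by study arm". Event types, severity, average duration, staff affected and schools affected follow, and the plan sets no common-source restriction on any of them.

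Section 8.2 introduces its safety table with "In each staff survey, we will assess the following variables". One row is labelled as emotional discomfort with PLANTS, but its description speaks more generally of the training program. Section 2.3.3 expects that distress could arise "as a result of intervention/control materials", so in either arm.

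**The concern.** Event counts set side by side by arm will be read as a comparison even if no test is attached. A fair reading needs events to be looked for equally hard in both arms. Here one named route is closed to EMAILS and a second is planned to reach more PLANTS staff. If true risk were equal, the expected all-source count would still be higher in PLANTS whenever those routes find anything the surveys miss.

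This matters because 8.2 describes most of these events as occurring across the country. The concurrent EMAILS arm is a main means of separating background events from those that follow the course. If source is not recorded as events occur, detection and true excess may not be separable afterwards.

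The discomfort row adds a second asymmetry. As labelled, it does not fit EMAILS staff, and it does not fit anyone at baseline, before training has begun.

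**Working it through.** **1. The plan's own figure.** Section 9.2 gives a 95% interval width of at most 0.21 for the proportion of PLANTS staff reporting adverse events, with n = 86 (344 × 0.5 × 0.5). The width is 2 × 1.96 × √(p(1−p)/n). At p = 0.5 this is 2 × 1.96 × √(0.25/86) = 0.211, which reproduces the figure with staff treated as independent. At p = 0.20 the width is 0.169. The plan gives no precision or power figure for any by-arm safety comparison.

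**2. Routes by arm, from the text.**

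| Route | PLANTS | EMAILS |
|---|---|---|
| Staff surveys (8.2) | yes | yes |
| Live Zoom Events (6.1.1, 8.3.4) | three, required | none |
| Interviews (9.2) | 20-30 | 10-20 |
| Contact about unfinished activities (6.4) | yes | not described |
| Questionnaire after each email (6.4) | not applicable | yes, on training completion |
| Retention and loss-to-follow-up contact (5.5, 7.3) | yes | yes |

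**3. Interview coverage at 86 per arm.** PLANTS: 20/86 = 23% to 30/86 = 35%. EMAILS: 10/86 = 12% to 20/86 = 23%. The ranges meet only at 20 interviews each.

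**4. Illustration of size.** Three inputs are assumptions that the documents do not give: true risk of 20% in both arms; survey sensitivity s of 0.5 to 0.9 among those who respond; and PLANTS-only routes finding a share e of 0.1 to 0.5 of what the survey misses. Survey completion of 75% is the 9.2 planning figure for PLANTS, applied here to both arms. With d = 0.75 × s:

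- EMAILS observed = 0.20 × d
- PLANTS observed = 0.20 × (d + (1 − d) × e)

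| s | e | EMAILS | PLANTS | Ratio | Excess per 86 |
|---|---|---|---|---|---|
| 0.5 | 0.1 | 7.5% | 8.75% | 1.17 | 1.1 |
| 0.5 | 0.5 | 7.5% | 13.75% | 1.83 | 5.4 |
| 0.7 | 0.1 | 10.5% | 11.45% | 1.09 | 0.8 |
| 0.7 | 0.5 | 10.5% | 15.25% | 1.45 | 4.1 |
| 0.9 | 0.1 | 13.5% | 14.15% | 1.05 | 0.6 |
| 0.9 | 0.5 | 13.5% | 16.75% | 1.24 | 2.8 |

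At e = 0, which is what identical survey items deliver, the channel-driven difference is zero if true risk, response and survey sensitivity are equal.

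**5. Schools affected.** Four schools randomized 1:1 give two per arm. A single event seen only in a Zoom session, in a school with no other report of that type, moves that arm's percentage of schools by 50 points. This matters mainly for rare event types.

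**6. Discomfort, if it were counted as an event in PLANTS only.** Assume a 15% rate of other events in both arms, with discomfort endorsed independently by a share q of PLANTS survey completers. The PLANTS rate is 1 − 0.85 × (1 − 0.75 × q). For q = 5%, 10% and 20% this gives 18.2%, 21.4% and 27.8%, against 15% in EMAILS. The documents do not state such a counting rule, so this shows only why one is needed.

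**The case against.** The strongest reply is that solicitation is largely symmetric. Direct questions are confined to surveys and interviews, and both arms receive both. The five safety endpoints in section 3 are survey items with no arm restriction. The Schedule of Activities (1.3) marks adverse event reporting in both program columns. Zoom sessions only may bring events to light. Some interviewees are chosen because they have already reported an event (8.2), so those interviews partly elaborate known events. All of this stands. It limits the size of the problem and makes the remedy easy, but it does not give EMAILS a counterpart to the Zoom route or restrict the pooled tables to common sources.

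A reader might infer more than the documents support:

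- *That EMAILS staff have no contact with the study.* The statement concerns interaction within the intervention, and email is excepted. Questionnaires follow each email, and retention contacts are not arm-specific.
- *That EMAILS is the only guide to background risk.* The backlash items are also asked at baseline in both arms.
- *That the discomfort item certainly inflates PLANTS counts.* This rests on a row label. The final wording is not given, no cut-off on its 5-point scale makes it an event, and it is not among the section 3 safety endpoints.
- *That the trial's safety hypothesis is undermined.* That hypothesis (at most 20%) concerns PLANTS alone. Extra detection raises the estimate and so works against declaring success.

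The by-arm safety analysis is also descriptive, so no type I error rate is at issue. Sections 4.1 and 6.3 acknowledge bias in adverse event reporting, but attribute it to lack of blinding, not to unequal routes of detection. Finally, the list of details in 8.3.4 may not be exhaustive. The form itself is not in the documents, and it may already capture source.

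**Conclusion.** The point holds as a limit on interpretation. Followed as written, the plan produces all-source by-arm tables that are tilted towards PLANTS to whatever extent Zoom sessions and additional interviews find events that surveys miss. The size cannot be derived from the documents. Under the assumptions shown, the spurious excess is 0.65 to 6.25 percentage points, with ratios of 1.05 to 1.83. Even the upper end lies inside the half-width of about 8.5 points for the PLANTS proportion alone at 20% (0.169/2), so it would not dominate sampling error. It is, however, systematic and avoidable.

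The discomfort variable is a separate and narrower drafting gap: its label names one arm, section 2.3.3 anticipates discomfort in both, and its status as an event is undefined. The change is worth making because it costs little, not because the trial's safety conclusion fails without it.

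**What to change.** 1. Add a field to the adverse event form for how the event first came to notice: survey, Live Zoom Event, interview or other contact.
2. In 9.4.4, make follow-up survey items asked in identical words in both arms the main basis for by-arm comparison.
3. Also show all-source totals, types, severity, duration and schools affected by arm, each split by source (survey versus Live Zoom Event, interview or other contact). Every event stays recorded and visible, including any severe event that no survey captured.
4. Word the discomfort item arm-neutrally, for example as discomfort with *the training materials you received*. Ask it at follow-up in both arms, and report it separately from event counts.

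The cost is one form field, one reworded item, a short addition to 9.4.4 and slightly smaller counts in the main comparison. The change removes only the imbalance between routes. Reporting bias from lack of blinding, which the protocol already acknowledges, would remain.
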